12.4 Laboratory Assessments

Laboratory assessment samples (Table 12-1) are to be obtained at designated visits as detailed in the Schedule of Assessments (Table 9-1).

| Hematology | Serum chemistry | Urine analysis (dipstick) | |
|---|-------------------------------------|------------------------------|--|
| Hemoglobin | Albumin | Appearance | |
| Hematocrit | Alanine aminotransferase (ALT) | Blood | |
| Platelet count | Alkaline phosphatase (ALP) | pН | |
| Red blood cell (RBC) count | Aspartate aminotransferase (AST) | Protein | |
| White blood cell (WBC) count | Blood urea nitrogen (BUN) or Urea | Glucose | |
| with differential | Bicarbonate | Ketones | |
| | Creatinine | Nitrite | |
| | Creatine kinase | Leukocyte esterase | |
| | Electrolytes (Na, K, Cl, Ca, P, Mg) | Specific gravity | |
| | Glucose | | |
| | Lactate dehydrogenase (LDH) | Urobilinogen | |
| | Total bilirubin | Bilirubin | |
| | Total protein | Microscopic, as | |
| | Uric acid | needed | |
| Coagulation | | | |
| Prothrombin time (PT), International Normalized Ratio | | | |
| (INR) | | | |
| Activated partial thromboplastin time (aPTT) | | | |
| Serum or Urine Pregnancy test: A pregnancy test will be performed on all female patients of | | | |

Table 12-1Laboratory Assessments

child-bearing potential at the screening visit and early termination visit.

The routine safety laboratory testing will be performed at the local laboratory following the lab's guidelines. PK, ADA and biomarkers will be analyzed at a qualified laboratory facility Urine samples will be analyzed by dipstick, and a microscopic analysis will be performed if the results of dipstick indicate abnormalities to be further investigated. All laboratory reports must be reviewed, signed, and dated by the Investigator. Any laboratory test result considered by the Investigator to be clinically significant should be considered an AE (clinically significant AEs include those that require an intervention). Clinically significant abnormal values occurring during the study will be followed until repeat test results return to normal, stabilize, or are no longer clinically significant.

12.5 Adverse Events

12.5.1 Adverse Events

An AE is any symptom, physical sign, syndrome, or disease that either emerges during the study or, if present at screening, worsens during the study, regardless of the suspected cause of the event. All medical and psychiatric conditions (except those related to the indication under study) present at screening will be documented in the medical history eCRF. Changes in these conditions and new symptoms, physical signs, syndromes, or diseases should be noted on the AE eCRF during the rest of the study. Clinically significant laboratory abnormalities should also be recorded as AEs. Surgical procedures that were planned before the patient enrolled in the study are not considered AEs if the conditions were known before study inclusion; the medical condition should be reported in the patient's medical history.

Patients will be instructed to report AEs at each study visit. All AEs are to be followed until resolution or until a stable clinical endpoint is reached.

Each AE is to be documented on the eCRF with reference to date of onset, duration, incidence, severity, relationship to study drug, action taken with study drug, treatment of event, and outcome. Furthermore, each AE is to be classified as being serious or non-serious. Changes in AEs and resolution dates are to be documented on the eCRF.

For the purpose of this study, the period of observation for collection of AEs extends from the time the patient receives the first dose of study treatment (Cycle 1 Day 1) until 28 days after end of treatment. Follow-up of the AE, even after the date of therapy discontinuation, is required if the AE persists until the event resolves or stabilizes at a level acceptable to the Investigator.

Specific guidelines for classifying AEs by intensity (Grade) and relationship to study drug are given in Table 12-2 and Table 12-3. The severity of AEs will be graded according to the NCI CTCAE version 4.03 (Grades 1 to 5).

Table 12-2 Classification of Adverse Events by Intensity (NCI CTCAE Grade)

MILD (Grade 1): An event that is easily tolerated by the patient, causing minimal discomfort, and not interfering with everyday activities.

MODERATE (Grade 2): An event that is sufficiently discomforting to interfere with normal everyday activities.

SEVERE (Grade 3): An event that prevents normal everyday activities.

LIFE-THREATENING (Grade 4)

DEATH (Grade 5)

Table 12-3 Classification of Adverse Events by Relationship to Study Drug

UNRELATED: This category applies to those AEs that are clearly and incontrovertibly due to extraneous causes (disease, environment, etc.).

UNLIKELY: This category applies to those AEs that are judged to be unrelated to the test drug, but for which no extraneous cause may be found. An AE may be considered unlikely to be related to study drug if or when it meets 2 of the following criteria: (1) it does not follow a reasonable temporal sequence from administration of the test drug; (2) it could readily have been produced by the patient's clinical state, environmental or toxic factors, or other modes of therapy administered to the patient; (3) it does not follow a known pattern of response to the test drug; or (4) it does not reappear or worsen when the drug is re-administered.

POSSIBLY: This category applies to those AEs for which a connection with the test drug administration appears unlikely but cannot be ruled out with certainty. An AE may be considered possibly related if or when it meets 2 of the following criteria: (1) it follows a reasonable temporal sequence from administration of the drug; (2) it could not readily have been produced by the patient's clinical state, environmental or toxic factors, or other modes of therapy administered to the patient; or (3) it follows a known pattern of response to the test drug.

PROBABLY: This category applies to those AEs that the Investigator feels with a high degree of certainty are related to the test drug. An AE may be considered probably related if or when it meets 3 of the following criteria: (1) it follows a reasonable temporal sequence from administration of the drug; (2) it could not be reasonably explained by the known characteristics of the patient's clinical state, environmental or toxic factors, or other modes of therapy administered to the patient; (3) it disappears or decreases on cessation or reduction in dose (note that there are exceptions when an AE does not disappear upon discontinuation of the drug, yet drug-relatedness clearly exists; for example, as in bone marrow depression, fixed drug eruptions, or tardive dyskinesia); or (4) it follows a known pattern of response to the test drug.

DEFINITELY: This category applies to those AEs that the Investigator feels are incontrovertibly related to test drug. An AE may be assigned an attribution of definitely related if or when it meets all of the following criteria: (1) it follows a reasonable temporal sequence from administration of the drug; (2) it could not be reasonably explained by the known characteristics of the patient's clinical state, environmental or toxic factors, or other modes of therapy administered to the patient; (3) it disappears or decreases on cessation or reduction in dose and recurs with re-exposure to drug (if re-challenge occurs); and (4) it follows a known pattern of response to the test drug.

When changes in the intensity of an AE occur more frequently than once a day, the maximum intensity for the event should be noted. If the intensity category changes over a number of days, then those changes should be recorded separately (with distinct onset dates).

The severity of AEs will be graded according to the NCI CTCAE version 4.03 (Grades 1 to 5).

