4.4 Clinical Risks/Benefits of OBI-888

As this is the first study in humans, there are no known clinical benefits that have been determined to be associated with the use of OBI-888. However, it is hoped that data from this clinical study and other trials sponsored by OBI Pharma will demonstrate the clinical benefits of OBI-888 in subjects with advanced or metastatic solid tumors.

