6.2 Definition of Dose-Limiting Toxicities

A DLT is defined as the occurrence of any of the following events, within the first cycle of treatment, that are considered to be at least possibly related to OBI-888. All AEs unless they have been determined to be not related to study drug will be taken into consideration in determining DLTs. NCI-CTCAE version 4.03 will be the basis for the descriptive terminology and grading of AEs.

DLTs are defined as:

- Grade 4 neutropenia
- *Erade 3 febrile neutropenia with or without infection*
- Grade 4 thrombocytopenia or Grade 3 thrombocytopenia with bleeding
- ≥Grade 3 nausea and vomiting or diarrhea for more than 72 hours despite optimal supportive care
- Any other ≥Grade 3 non-hematological AE that does not resolve before the next infusion.

The DLT evaluation period is the first cycle; 28 days from start of study treatment.

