10.7.1 PRIMARY ENDPOINTS

A. DLTs with OBI-888

The period for DLT is 28 days from the start of first dose of Investigational Product at Day 1 in study part A.

A DLT is defined as the occurrence of any of the following events within the first cycle of treatment and are considered to be at least possibly related to OBI-888:

- Grade 4 neutropenia
- Grade ≥ 3 febrile neutropenia with or without infection
- Grade 4 thrombocytopenia
- Grade ≥ 3 nausea and vomiting or diarrhea for more than 72 hours despite optimal supportive care
- Any Grade ≥ 3 non-hematological AE, except for nausea, vomiting, or diarrhea that does not resolve before the next infusion
- Grade 4 infusion reactions, and Grade ≥ 3 infusion reactions that recur despite decreasing infusion rate and optimal supportive care measures

DLTs will be displayed by assigned dose and cohort in a frequency table in decreasing order of incidence. DLTs will not be programmatically derived but analyzed as collected on the eCRF.

AE terms will be coded using the most current version of the Medical Dictionary for Regulatory Activities (MedDRA). AEs will be graded according to the NCI CTCAE version 4.03. All AEs unless they have been determined to be not related to study drug will be taken into consideration in determining DLTs.

B. AEs/SAEs and laboratory abnormalities as graded by NCI CTCAE version 4.03

A treatment-emergent adverse event (TEAE) is defined as an AE with onset dates on or after the start of study drug or if it is present prior to receipt of the study treatment but worsens in severity or increases in frequency on or after the first dose. AEs having both onset and end dates missing will be considered as TEAEs.

Events reported as "Unrelated" or "Unlikely related" to study drug will be considered as unrelated to the study drug. Events reported as "Possibly related", "Probably related", "Definitely related" to study drug or without relationship information will be considered as related to the treatment.

Tables will display the incidence of events (number of events, number of patients with any event, number of patients with any event in each specific system organ class [SOC], and number of patients with any event for each specific preferred term [PT]).

For each AE, only the highest grade and closest association with study drug by patient will be considered in the incidence analyses.

The following tables will be produced:

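### Table 12-3's relatedness criteria contradict their own definitions, so the related-event tables can undercount and it is unclear whether events rated Unlikely can be DLTs

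*Protocol*

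**What the plan says.** **Relatedness scale (protocol 12.5.1, Table 12-3).** For the middle category: "An AE may be considered possibly related if or when it meets 2 of the following criteria". The three criteria are that timing fits, that "it could not readily have been produced by the patient's clinical state, environmental or toxic factors, or other modes of therapy", and that "it follows a known pattern of response to the test drug". The sentence introducing the category is wider: it covers events whose link to the drug looks improbable but cannot be fully excluded.

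For the category below: "An AE may be considered unlikely to be related to study drug if or when it meets 2 of the following criteria". The four criteria are that timing does not fit, that "it could readily have been produced by the patient's clinical state" (or by environment or other therapy), that there is no known drug pattern, and that the event does not return or worsen on re-administration. The sentence introducing this category says that no outside cause can be identified.

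**Use in the tables (SAP 10.7.1 B).** Events reported as Unrelated or Unlikely related "to study drug will be considered as unrelated to the study drug". Possibly, Probably, Definitely and missing all count as related. Among the SOC/PT tables, the related-serious table is starred for the abbreviated report. The all-cause serious table is not starred, and SAP section 11 lists serious TEAEs among the summaries dropped.

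**Use in the DLT definition (protocol 6.2, repeated in SAP 10.7.1 A).** The first sentence limits DLTs to listed events "that are considered to be at least possibly related to OBI-888". The next takes into consideration every AE except those determined not to be related. The SAP reports DLTs as recorded on the eCRF and does not derive them.

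**Setting.** Protocol 4.4 opens "As this is the first study in humans". Protocol 4.3.1 reports no DLTs in Part A and, as of March 2020, 8 SAEs, all assessed by the Investigator as unrelated.

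**The concern.** Early in a drug's clinical development, the absence of a known toxicity pattern says little about causality. Table 12-3 nevertheless counts it towards Unlikely and withholds a point from Possibly. In advanced cancer an alternative explanation will often be available, and that is scored the same way. An event can therefore have credible timing, a drug cause that nobody can exclude, and still satisfy only the Unlikely count.

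The rating feeds two outputs. It decides directly whether an event enters the related-TEAE and related-serious-TEAE tables. Under one reading of section 6.2 it also decides whether a Cycle 1 event can be a DLT. DLTs and AEs are primary endpoints, and the absence of DLTs is the stated reason for starting Part B at the highest dose tested. If the rating rule is unclear, the reader cannot tell how far these results depend on attribution.

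**Working it through.** The plan gives no figure on this point, so there is nothing to reproduce. The check has three steps.

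**1. Count the criteria.** Code an event by five yes/no features: T (timing fits), D (ready disease or other explanation), K (known drug pattern), C (improves when the drug is stopped or reduced), R (returns or worsens on re-administration). From Table 12-3:

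- Unlikely: (not T) + D + (not K) + (not R) ≥ 2
- Possibly: T + (not D) + K ≥ 2
- Probably: T + (not D) + C + K ≥ 3

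Definitely needs every one of its criteria, including no alternative explanation and a known pattern. Unrelated has no count; it requires a clear and incontrovertible outside cause.

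| Event | Possibly (needs 2 of 3) | Unlikely (needs 2 of 4) | Probably (needs 3 of 4) |
|---|---|---|---|
| T yes, D yes, K no | 1: not met | 2 or 3: met | 1 or 2: not met |
| T yes, D no, K no, R yes | 2: met | 1: not met | 2 or 3: met only if C |
| T yes, D no, K no, R no | 2: met | 2: met | 2 or 3: met only if C |

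In the first row, Unlikely is the only count met, even when the event improves off drug and returns on re-administration. In the third row, Possibly and Unlikely are both met. Over all 32 combinations, 6 meet both counts (three of these also meet Probably). The table gives no tie-break. These are logical combinations, not frequencies of real events.

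**2. Set the definitions beside the counts.**

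- *Unlikely:* the introduction requires that no outside cause be identified; criterion 2 is that one is readily available.
- *Possibly:* the introduction asks only that a link cannot be excluded. Any two of its three criteria must include either the absence of a ready alternative or a known pattern, so the count is narrower.
- *DLT sentences:* the first excludes Unlikely. The second excludes it only if Unlikely means determined to be not related. The Unlikely introduction, which describes such events as judged unrelated, and the SAP pooling both lean that way, but section 6.2 does not say so.

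**3. Illustrate what attribution could do to a 3+3 decision.** A level passes with 0 of 3 DLTs, or with 1 of 3 followed by 0 of 3 (protocol 6.1.1). With recorded DLT rate q = p × (1 − m), where p is the true rate and m the share of DLTs rated Unlikely and not counted:

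P(pass) = (1 − q)³ + 3q(1 − q)⁵

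Both p and m are assumptions; neither is in the documents.

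| True rate p | m = 0 | m = 25% | m = 50% |
|---|---|---|---|
| 20% | 0.71 | 0.81 | 0.91 |
| 33% | 0.43 | 0.61 | 0.78 |
| 50% | 0.17 | 0.35 | 0.60 |

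For p = 33% and m = 50%, q = 0.165: 0.835³ + 3 × 0.165 × 0.835⁵ = 0.582 + 0.201 = 0.78.

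**The case against.** Four objections carry weight.

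- **The scale is guidance.** The criteria say what an investigator may consider, and section 12.5.1 calls them guidelines. An investigator who follows the introductory sentences would rate the problem case Possibly. This stands: the text contradicts itself and does not force one answer. A reader might infer that plausible toxicity generally defaults to Unlikely. The documents do not support that, because fitting timing with no ready alternative cause already reaches Possibly without any known pattern.
- **Some pattern is known.** Section 8.3.1 lists infusion-reaction signs, section 4.2 gives nonclinical findings, and Part B can draw on Part A. This narrows the affected events but does not remove them.
- **The SAP pooling does not set DLT counts.** They come from the eCRF, and the Safety Review Committee determines whether DLTs have occurred. This is correct. The route to DLTs is attribution under section 6.2, and that section is ambiguous. It cannot be said that the DLT rule plainly treats Unlikely as unrelated.
- **All-cause outputs remain.** All TEAEs, Grade 3 or higher TEAEs, and TEAEs leading to discontinuation or death are tabulated, and all SAEs are listed. Of the 8 SAEs in section 4.3.1, two were Grade 5 and six Grade 3, so if treatment-emergent they would enter the Grade 3 or higher table. This limits the loss of information. It does not supply an all-cause count by seriousness, and it does not show how the related tables change if Unlikely is counted.

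Missing relationship is counted as related, which pushes the other way, and events meeting both counts may be placed in either category. A one-directional bias is therefore not established.

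**Conclusion.** The defect is real and limited. Table 12-3's counts conflict with its own definitions and overlap without a tie-break. In one defined case (fitting timing, ready disease explanation, no known pattern) only the Unlikely count is met. The SAP then treats such an event as unrelated, so the related-TEAE and related-serious-TEAE tables can undercount while no all-cause serious table is produced. Separately, protocol 6.2 and SAP 10.7.1 A leave open whether events rated Unlikely can be DLTs.

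The size is unknown. The 0.43, 0.61 and 0.78 figures rest on an assumed 33% true rate, on assumed shares rated Unlikely, and on the reading of 6.2 that excludes such events.

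A reader might infer that the zero-DLT result in Part A is an artefact of attribution. The documents do not show this. No event is shown to be misclassified, and no DLTs with all 8 SAEs assessed as unrelated fits either reading. The documents also do not say how many events, if any, were rated Unlikely. What can be said is that the planned tables do not let a reader test the dependence.

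**What to change.** 1. **Reconcile the text.** Bring the Table 12-3 criteria into line with their introductory sentences and state a tie-break for events that meet more than one category. Reconcile the two attribution sentences in protocol 6.2 and SAP 10.7.1 A so that the status of Unlikely events is explicit. Part A is complete, so rewording cannot change attributions already made there; items 2 and 3 address those.
2. **Add a column.** In the related-TEAE and related-serious-TEAE tables (SAP 10.7.1 B), show counts with Unlikely treated as related beside the planned counts.
3. **Add a short listing.** From the AE data already collected, list Part A Cycle 1 AEs of Grade 3 or higher rated Unlikely, and report whether the zero-DLT result holds under both readings of section 6.2.

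Cost: wording changes, one extra column in two tables and one short listing, with no new data. The related-AE figures may look somewhat less favourable.

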12.5.2 Serious Adverse Events

An AE is considered "serious" if in the view of either the Investigator or Sponsor, it meets one or more of the following criteria:

- Is fatal
- Is life-threatening
- Results in inpatient hospitalization or prolongation of existing hospitalization
- Results in a persistent or significant incapacity or substantial disruption of the ability to conduct normal life functions
- Is a congenital anomaly/birth defect

Other important medical events that may not be immediately life-threatening or result in death or hospitalization, based upon appropriate medical judgment, are considered SAEs if they are thought to jeopardize the patient and/or require medical or surgical intervention to prevent one of the outcomes defining a SAE.

Since SAEs are critically important for the identification of significant safety problems, it is important to take into account both the Investigator's and the Sponsor's assessment. If either the Sponsor or the Investigator believes that an event is serious, the event must be considered serious and evaluated by the Sponsor for expedited reporting.

Hospitalization is not considered an SAE and should not be reported if it is for social reasons in the absence of an AE, or for diagnostic or study-related procedures.

Disease progression is considered an expected event in this patient population, and should not be considered an AE or SAE. However, any medical event/condition that is untoward in the context of disease progression and/or for the specific patient's disease course should be reported as an AE and assessed accordingly by the investigator.

Progression of disease with a fatal outcome does not need to be reported as an AE. However the applicable protocol CRF page(s) pertaining to death should be completed immediately in order to record the disease progression/death.

12.5.3 Serious Adverse Event Reporting

An SAE occurring after receiving OBI-888 or within 28 days of stopping the treatment must be reported to the contracted contract research organization (CRO) and will be communicated to the Sponsor. Any such SAE due to any cause, whether or not related to the study drug, must be reported within 24 hours of occurrence or when the Investigator becomes aware of the event. The Investigator must send the SAE information to the Sponsor/contracted CRO using the electronic data system (preferred method), by filling out a paper SAE reporting form (to be sent via electronic mail or dedicated fax line), or by telephone line. SAEs occurring after signing of the informed consent before and before receiving OBI-888 should be reported only if the SAE was directly related to a screening procedure.

If the Investigator contacts the contracted CRO by telephone, then a written report must follow within 24 hours and is to include a full description of the event and sequelae in the AE report page of the eCRF.

The event must also be recorded on the standard AE eCRF. Preliminary reports of SAEs must be followed by detailed descriptions later on, including clear and anonymized photocopies of hospital case reports, consultant reports, autopsy reports, and other documents when requested and applicable. SAE reports must be made whether or not the Investigator considers the event to be related to the investigational drug.

Appropriate remedial measures should be taken to treat the SAE, and the response should be recorded. Clinical, laboratory, and diagnostic measures should be employed as needed in order to determine the etiology of the problem. The Investigator must report all additional follow-up evaluations to the contracted CRO within 10 calendar days. All SAEs will be followed until the Investigator and Sponsor agree the event is satisfactorily resolved.

Any SAE that is not resolved by the end of the study or upon discontinuation of the patient's participation in the study is to be followed until it either resolves, stabilizes, returns to baseline values (if a baseline value is available), or is shown to not be attributable to the study drug or procedures.

